6. STUDY PROCEDURES

Enrollment Visit (60 minutes)

Subjects will be enrolled at the Brigham MS Center at the Brigham and Women's Hospital. At enrollment, subjects will be consented and assigned a study subject ID. Subjects will complete a battery of PRO measures in REDCap, a secure web application for building and managing online surveys. The PRO measures include:

1. Positive and Negative Affect Scale (PANAS) [11] is comprised of two 10-item mood scales, one measuring positive affect and the other negative affect.
2. Life Orientation Test-Revised (LOT-R) [12] is a 6-item measure of optimism and pessimism and the most widely used measure of optimism.

3. NeuroQoL [13] is a set of self-report measures developed through a collaborative, multisite NINDS-sponsored research initiative to construct psychometrically-sound and clinically-relevant HRQOL tools for individuals with neurological conditions such as stroke, MS and Parkinson's disease. It covers 12 domains including Ability to Participate in Social Roles and Activities, Anxiety, Cognitive Function, Depression, Emotional and Behavioral Dyscontrol, Fatigue, Lower Extremity Function, Positive Affect and Well-Being, Satisfaction with Social Roles and Activities, Sleep, Stigma and Upper Extremity Function.
4. Brief Resilience Scale (BRS) [14] is a 6-item scale that measures the ability to bounce back or recover from stress.

After enrollment, a computerized random number generator will be used to randomize subjects to the intervention or control group.

Intervention Phase (5 weeks)

In the intervention phase (Phase I: Weeks 1-5), subjects randomized to the intervention group will be given the study participant manual and asked to set up a time for weekly phone calls with the study coordinator. They will complete five weeks of PP exercises, one exercise per week. They will be asked to rate their mood prior to and after completing each exercise. They will also be asked to rate the ease and utility of each exercise. The weekly calls with the study coordinator will be used to document and discuss the ease and utility scores recorded by subjects at the completion of the weekly exercise. The control group will have no study activities during the intervention phase and will be considered a wait-list control. At the completion of the intervention phase, all subjects will be emailed a link to complete PRO measures in REDCap.

Extension Phase (5 weeks)

In the extension phase (Phase II: Weeks 6-10), subjects in the control group will receive their study participant manual in the mail. They will be contacted by the study coordinator to set up weekly phone calls. They will complete the PP intervention as described above. The intervention group will complete no study activities in the extension phase. At the completion of the extension phase, all subjects will be emailed a link to complete PRO measures.

Intervention: The PP intervention consists of five weeks of self-directed PP training using the following exercises:

1. Gratitude for positive events: Recall three positive events that occurred in the past week and write about the events and how the events made you feel.
2. Personal strengths: Complete a brief survey of personal strengths and select a strength such as perseverance or humility and use it deliberately in the next 24 hours. Write about how you used the strength and how you felt while using it.

3. Gratitude letter: Recall another individual's kind act that resulted in joy, relief, serenity or other positive feelings. Write a letter to the person describing feelings of gratitude associated with this event.
4. Enjoyable and meaningful activities: Intentionally complete three acts in a single day – a pleasurable act done alone, a pleasurable act done with others and a meaningful or important act.
5. Remembering past successes: Focus on a time when you experienced success and write about the event and the positive feelings and thoughts you had during the event

These exercises have all been described by Huffman et al. [10, 15]. Exercises may require anywhere from 15 minutes to several hours to complete.

7. Risks and Discomforts

There are no major risks associated with participating in the study. Subjects may experience discomfort writing about emotional aspects of their lives. If they do experience discomfort, they may choose not to complete the weekly PP assignments. If they feel their participation is becoming too burdensome or is exacerbating ongoing symptoms, they have the option to decline further participation and withdraw from the study. They may also be referred to a mental health provider at the Brigham MS Center.

8. Benefits

This is a pilot study designed to determine the feasibility, acceptability and efficacy of a self-directed PP training program for individuals with newly diagnosed MS. If the results suggest that self-directed PP training is feasible, acceptable and effective, it may be offered as a no cost, innovative tool for increasing positive affect, decreasing depression and anxiety and improving HRQOL in patients with newly diagnosed MS.

9. Statistical Analysis

To assess the feasibility of the intervention (Specific Aim 1), our goal is to demonstrate that the proportion who will complete four out of five exercises is greater than 0.5. Given our sample size of 30 subjects, we will have 80% power to detect a difference if the true proportion of subjects who will complete four out of five exercises is 0.75 using a one sample binomial test of proportions (Stata routine: *power oneproportion*). For the comparison of the treatment groups in terms of PRO measures (Specific Aim 2), the intervention effect will be estimated using analysis of covariance (ANCOVA) model. In the ANCOVA model, the post-intervention scores

will be compared between the groups controlling for baseline scores. All outcome measures (PANAS, LOT-R, NeuroQoL and BRS) will be compared using the same model. To assess whether benefits of the PP intervention are maintained at 10 weeks (Specific Aim 3), we will first calculate the change from baseline to week 5 for each of the outcome measures. For the subjects who experience a benefit of the intervention, we will then assess if at least 50% of the benefit was maintained at the 10-week time point. The proportion of subjects who maintained the benefit will be reported.

10. Monitoring and Quality Assurance

[name], the PI, will be responsible for assuring the validity and integrity of the data collected, and adherence to the IRB-approved protocol. The study team will meet weekly to review subject recruitment, subject satisfaction and study progress. Adverse events associated with the study will be reported to the PI within 24 hours of knowledge of the event. The PI will report adverse events or other unanticipated problems to PHRC as described in the PHRC policy on Adverse Event Reporting and Unanticipated Problems Involving Risks to Subjects or Others.

11. Privacy and Confidentiality

- Study procedures will be conducted in a private setting
- Only data and/or specimens necessary for the conduct of the study will be collected
- Data collected (paper and/or electronic) will be maintained in a secure location with appropriate protections such as password protection, encryption, physical security measures (locked files/areas)
- Specimens collected will be maintained in a secure location with appropriate protections (e.g. locked storage spaces, laboratory areas)
- Data and specimens will only be shared with individuals who are members of the IRB-approved research team or approved for sharing as described in this IRB protocol
- Data and/or specimens requiring transportation from one location or electronic space to another will be transported only in a secure manner (e.g. encrypted files, password protection, using chain-of-custody procedures, etc.)
- All electronic communication with participants will comply with Mass General Brigham secure communication policies
- Identifiers will be coded or removed as soon as feasible and access to files linking identifiers with coded data or specimens will be limited to the minimal necessary members of the research team required to conduct the research
- All staff are trained on and will follow the Mass General Brigham policies and procedures for maintaining appropriate confidentiality of research data and specimens
- The PI will ensure that all staff implement and follow any Research Information Service Office (RISO) requirements for this research
- Additional privacy and/or confidentiality protections

12. References

1. Marrie, R.A., et al., *The burden of mental comorbidity in multiple sclerosis: frequent, underdiagnosed, and undertreated*. Mult Scler, 2009. **15**(3): p. 385-92.
2. Korostil, M. and A. Feinstein, *Anxiety disorders and their clinical correlates in multiple sclerosis patients*. Mult Scler, 2007. **13**(1): p. 67-72.
4. Healy, B.C., et al., *The impact of a recent relapse on patient-reported outcomes in subjects with multiple sclerosis*. Qual Life Res, 2012. **21**(10): p. 1677-84.
5. Dennison, L., R. Moss-Morris, and T. Chalder, *A review of psychological correlates of adjustment in patients with multiple sclerosis*. Clin Psychol Rev, 2009. **29**(2): p. 141-53.
6. Seligman, M.E.P., *Learned Optimism: How to Change Your mind and Your Life*. 1991, New York: Alfred A. Knopf.

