We would like to evaluate the feasibility, acceptability and efficacy of a self-guided version of the PP intervention in individuals with recently diagnosed with MS. An MS diagnosis creates a crisis for the individual and his/her family. Typical initial emotional responses include fear, denial, anger and resentment [9]. The introduction of techniques to increase positive emotional experiences early on in the disease course might promote successful adaptation to living with MS. If we are able to demonstrate the feasibility, acceptability and efficacy of a self-

directed PP program, it could be made available to all newly diagnosed patients seen at the Brigham Multiple Sclerosis Center.

2. Specific Aims and Objectives

Specific Aim 1: Evaluate the feasibility and acceptability of a five-week self-directed PP training intervention for newly diagnosed patients with MS. We will assess the feasibility of the intervention by calculating the proportion of subjects who complete four of the five weekly exercises. We will determine the acceptability of each exercise by having subjects rate the ease and utility of each exercise after it is completed.

[figure not shown]
Specific Aim 2: Examine the efficacy of PP training to improve positive affect, emotional function and HRQOL. We will compare positive affect in subjects in the intervention and control group at the completion of the intervention phase. We will also assess between-group differences in depression, anxiety, fatigue, resilience and HRQOL following the intervention phase.

Specific Aim 3: Determine if improvements in positive affect, emotional function and HRQOL following PP training are maintained. For subjects in the intervention group who demonstrate a benefit from PP intervention, we will determine if that benefit is maintained by comparing positive affect, depression, anxiety, fatigue, resilience and HRQOL at the completion of the intervention and extension phases.

3. General Description of Study Design

This is a phase I randomized controlled trial (RCT) to examine the feasibility, acceptability and efficacy of a self-directed PP training intervention to increase positive affect in newly diagnosed patients with MS. The RCT will include a five-week intervention phase and a five-week extension phase.

Schema:

4. Subject Selection

Thirty subjects with newly diagnosed MS will be enrolled at the Brigham MS Center.

Inclusion criteria:

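### Section 7 does not separate stopping the exercises from leaving questionnaire follow-up, so loss confined to the intervention arm could bias the Aim 2 comparison, plausibly but not certainly towards positive psychology

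*Combined protocol and SAP*

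**What the plan says.** Section 7 (Risks and Discomforts) gives three responses to difficulty with the programme.

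- For discomfort when writing about emotional matters: "If they do experience discomfort, they may choose not to complete the weekly PP assignments".
- For participation that is too burdensome or that worsens existing symptoms: "they have the option to decline further participation and withdraw from the study".
- As a further possibility: "They may also be referred to a mental health provider at the Brigham MS Center".

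Section 6 (Intervention Phase) says of the other arm: "The control group will have no study activities during the intervention phase and will be considered a wait-list control". It then says: "At the completion of the intervention phase, all subjects will be emailed a link to complete PRO measures in REDCap". The Extension Phase text sends a second link to all subjects at its end.

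Under Section 9, Aim 2 is an ANCOVA in which post-intervention scores "will be compared between the groups controlling for baseline scores". The section defines no analysis set and has no rule for missing week-5 scores. Neither it nor Sections 6 and 7 say whether questionnaires are still sought from a subject who has withdrawn.

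**The concern.** Three features combine.

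1. For burden or worsening symptoms, the route named in Section 7 is departure from the study. No text describes a subject who gives up the exercises and calls for that reason but still answers the questionnaires. The link goes to all subjects, but the plan does not say whether someone who has withdrawn still counts as one.
2. Until week 5 the wait-list arm has no exercises and no calls. Controls can leave for other reasons, but not because of the programme.
3. The reason for leaving is close to what is measured. Aim 2 compares positive affect, depression, anxiety, fatigue, resilience and quality of life, and a subject whose symptoms are getting worse is likely to score poorly on some of these.

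An ANCOVA on week-5 scores omits anyone without one. If those omitted did worse than their baseline predicted, the rest of the intervention arm looks better than the arm as randomised. Adjusting for baseline does not remove a difference that arose during the exercises. With 30 subjects in all, two or three losses in one arm matter. Section 8 says that the programme may be offered to patients if it appears feasible, acceptable and effective.

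**Working it through.** **The plan's own figure.** No figure in the documents bears on this point. The only power statement (Section 9, Aim 1) is 80% for 30 subjects, 0.5 against 0.75. At an assumed two-sided 0.05 it reproduces: 0.803 by the exact binomial test (success at 21 or more of 30) and 0.816 by the score test. No power or dropout rate is given for Aim 2, so the size of the bias can only be illustrated.

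**Inputs.** From the documents: 30 subjects, ANCOVA on the post-intervention score adjusted for baseline, no exercises in the control arm before week 5. Assumed: 15 per arm (no ratio is stated), score SD 1 with higher meaning better, baseline to week-5 correlation r = 0.6, no true effect, k of 15 intervention subjects without a week-5 score, and correlation c between tendency to leave and a poor week-5 score given baseline.

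**Formula.** The residual SD given baseline is √(1 − 0.6²) = 0.8. If the k subjects most inclined to leave are lost, the mean of those who remain shifts by

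shift = c × 0.8 × A(k), where A(k) = −(sum of the k lowest expected normal order statistics of 15) / (15 − k).

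The three lowest are −1.736, −1.248 and −0.948, so:

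- A(1) = 1.736/14 = 0.124
- A(2) = 2.984/13 = 0.230
- A(3) = 3.932/12 = 0.328

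| Lost of 15 | c = 0.5 | c = 1 (exactly the worst leave) | c = 0 | c = −0.5 (better responders leave) |
|---|---|---|---|---|
| 1 | +0.05 | +0.10 | 0 | −0.05 |
| 2 | +0.09 | +0.18 | 0 | −0.09 |
| 3 | +0.13 | +0.26 | 0 | −0.13 |

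Entries are in SD; positive favours PP. Simulated ANCOVAs agree to within about 0.01 SD.

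**Chance of a falsely favourable significant result** (two-sided 0.05, simulated). With no loss it is about 2.5%. With three lost it is 6% to 7% at c = 0.5 and 15% at c = 1.

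**If controls leave too.** With three intervention subjects and two controls lost, both at c = 0.5, the shift is 0.131 − 0.092 = about +0.04 SD.

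**If the programme is mildly harmful.** With a true effect of −0.2 SD and three lost, the mean estimate is −0.2 + 0.13 = −0.07 SD at c = 0.5. At c = 1 it is −0.2 + 0.26 = +0.06 SD, with about 5% falsely favourable results.

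**The case against.** The text can be read more generously. The sentence on discomfort lets a subject skip assignments, with no stated limit, and remain enrolled. Aim 1 expects incomplete participation, since feasibility is assessed by "calculating the proportion of subjects who complete four of the five weekly exercises". The week-5 link does not depend on exercises completed, nothing restricts the ANCOVA to completers, and withdrawal is worded as an option. All of this stands. A reader might infer that leaving the study is the only choice open to a struggling subject, and the documents do not support that. What remains is that skipping is tied to discomfort, while burden and worsening symptoms are treated separately and lead to withdrawal.

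The direction is also open. Burden may be a matter of time, since an exercise can take several hours, and time need not relate to outcome. Existing symptoms may already show in the baseline score. Controls may withdraw or ignore an emailed link. A reader might infer that the bias must favour PP; the table shows that it can be zero or reversed. The most that can be said is that the stated reasons for leaving make loss of poor responders the more plausible case.

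Two further inferences go too far. One is that a harmful programme would look helpful: for a −0.2 SD effect with three lost, the mean estimate turns positive only in the extreme case, where exactly the three worst leave. That is unlikely to hold at once across outcomes as different as optimism and upper-extremity function. The other is that the selection carries into Aim 3. That aim starts from subjects who had benefited by week 5, and those who left because they worsened would not have been among them.

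Finally, this is a small pilot whose only powered aim is feasibility, and at c = 0.5 with three lost the shift is under half the ANCOVA standard error of about 0.31 SD. That limits the weight of the point but does not remove it, because Aim 2 is a stated efficacy comparison. Consent pages are not available here and may address follow-up after withdrawal.

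**Conclusion.** The point holds in a limited form. For burden or worsening symptoms the plan offers withdrawal without distinguishing it from stopping the exercises and calls. Before week 5 this source of loss exists in one arm only, and Section 9 neither says how missing week-5 scores are handled nor tests their effect. The Aim 2 estimates could be biased, plausibly but not certainly towards PP.

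Illustrative size: about 0.05 to 0.26 SD with 1 to 3 of 15 intervention subjects lost and leaving related to poor outcome, and near zero if leaving is unrelated to outcome or controls leave similarly. These figures rest on assumed equal allocation, loss counts and correlations; the documents give none of them. The change is worth making because it is cheap and must be in place before week-5 data are collected.

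**What to change.** Leave the subject's right to stop or withdraw exactly as it is.

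- **Sections 6 and 7.** State that a subject who stops the exercises or calls stays enrolled and is sent the week-5 and week-10 REDCap links unless he or she also declines the questionnaires. Check that the consent wording agrees.
- **Section 9, analysis set.** State that the ANCOVA includes all randomised subjects with week-5 data, in their assigned arm, whatever number of exercises they completed.
- **Section 9, reporting.** Report missing week-5 questionnaires by arm and reason.
- **Section 9, sensitivity.** Prespecify one missing-not-at-random analysis: impute missing week-5 scores in both arms from baseline and arm, add a shift (delta), and vary it over a stated range in each arm. As a guide, the bias is the fraction lost times the leaver-to-stayer difference. The three-lost cases above correspond to differences of 0.13/(3/15) = about 0.65 SD and 0.26/(3/15) = 1.3 SD, so a range from 0 to 1.3 SD worse would cover both.

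Cost: a few sentences of protocol wording and one extra analysis. The links are already part of the design, so no visits are added. The estimated effect may be somewhat smaller, because subjects who did few exercises are included.

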APPENDIX A

Data Monitoring Committee / Data and Safety Monitoring Board Appendix

- *To be completed for studies monitored by Data Monitoring Committee (DMC) or Data and Safety Monitoring Board (DSMB) if a full DMC/DSMB charter is not available at the time of initial IRB review.*
- *DMC/DSMB Charter and/or Roster can be submitted to the IRB later via Amendment, though these are not required.*

A Data Monitoring Committee (DMC) or Data and Safety Monitoring Board (DSMB) will be convened for safety monitoring of this research study. The following characteristics describe the DMC/DSMB convened for this study (Check all that apply):

- The DMC/DSMB is independent from the study team and study sponsor.
- A process has been implemented to ensure absence of conflicts of interest by DMC/DSMB members.
- The DMC/DSMB has the authority to intervene on study progress in the event of safety concerns, e.g., to suspend or terminate a study if new safety concerns have been identified or need to be investigated.
- Describe number and types of (i.e., qualifications of) members:**

Click or tap here to enter text.
- Describe planned frequency of meetings:**

Click or tap here to enter text.
- DMC/DSMB reports with no findings (i.e., “continue without modifications”) will be submitted to the IRB at the time of Continuing Review.
- DMC/DSMB reports with findings/modifications required will be submitted promptly (within 5 business days/7 calendar days of becoming aware) to the IRB as an Other Event.
